16.2 Secondary Endpoint Analyses

Analysis set: ITT analysis set, PP analysis set

The secondary endpoints include:

- Duration of response (IERC);
- Progression free survival (PFS) time according to RECIST 1.1 as determined by an IERC,
- Overall survival (OS) time;
- Response status according to RECIST 1.1 at 6 and 12 months after start of study treatment.

For imputing missing parts of dates for the secondary efficacy endpoints the missing day in a date will be imputed as the 15th of the month, if month and year are documented. If the imputation is earlier than the date of first study treatment, then the day of first study treatment is taken. In all other cases missing or incomplete dates will not be imputed.

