16.2.1 Duration of Response (IERC)

The duration of response will be calculated for each subject with a confirmed response according to RECIST 1.1 as the time from first observation of response until first observation of documented disease progression or death when death occurs within 12 weeks of the last tumor assessment, whichever occurs first. Details on determination of the first disease progression date are specified in the IERC charter. For subjects with a confirmed response but neither documented disease progression nor death within 12 weeks after the last tumor assessment, as of the cut-off date for the analysis, the duration of response will be censored at the date of the last adequate tumor assessment.

Duration of response = (date of PD or death – date of objective response + 1)/30.4375 (months).

The Kaplan-Meier method will be used to estimate parameters for duration of response. Kaplan-Meier estimates (product-limit estimates) will be presented together with a summary of associated statistics including corresponding two-sided 95% CIs. In particular, the proportion of duration of responses at 3, 6 and 12 months will be estimated with corresponding two-sided 95% CIs. The CIs for the median will be calculated according to Brookmeyer and Crowley (2) and CIs for the survival function estimates at the above defined time points will be derived using the log-log transformation according to Kalbfleisch and Prentice (3) (CONFTYPE = loglog default option in SAS PROC LIFETEST). The estimate of the standard error will be computed using Greenwood's formula.

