16.2.3 Overall Survival

The overall survival (OS) time will be defined as the time from first administration of trial treatment until the date of death.

For subjects who are still alive at the time of data analysis or who are lost to follow up, OS time will be censored at the last recorded date that the subject is known to be alive (date of last contact, last visit date, date of last trial treatment administration or date of last scan, whichever is the latest) as of the data cut-off date for the analysis.

OS = (date of death – date of the first dose of study treatment + 1)/30.4375 (months).

The analysis of OS time will be performed using a Kaplan-Meier method with the same approach as for duration of response described in Section 16.2.1. Kaplan-Meier estimates (product-limit estimates) will be presented together with a summary of associated statistics including corresponding two-sided 95% CIs. In particular, the proportion of overall survival at 3, 6 and 12 months will be estimated with corresponding two-sided 95% CIs.

The OS time will also be presented in a subject listing.

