 - = Last day of the month, if both Year and Month are available and Year = Year of min (EOT date, death date) and Month < the month of min (EOT date, death date)
 - = min (EOT date, death date), for all other cases

Date of last contact

The last contact date will be the latest complete date among the following, up to the cut-off date for the analysis:

- All subject assessment dates (blood draws (laboratory, PK), vital signs, performance status, ECG, tumor assessments)
- Start and end dates of anti-cancer therapies administered after study treatment discontinuation
- AE start and end dates
- Date last known to be alive collected on the eCRF form “Subject Status / Survival Follow-up” (only used if status is ‘alive’)
- Study drug start and end dates
- Date of discontinuation from the “Study Termination” eCRF page (do not use if reason for discontinuation is lost to follow-up)

Death date

Missing or partial death dates will be imputed based on the last contact date.

- If the date is completely missing it will be imputed as the day after the date of last contact.
- If the day or month is missing, death will be imputed to the maximum of the full (non-imputed) date of last contact (excluding the date of death) and the following:
 - Missing day: 1st day of the month and year of death
 - Missing day and month: January 1st of the year of death

If the day is missing from the date of last contact it will be imputed to 1st day of the month and year of last contact only if derived from the survival page.

Tumor assessments

The following specifications apply to the determination of tumor assessment date for investigator assessment. For tumor assessments by the IERC, the date of assessment is determined by the IERC as specified in the Charter.

All investigation dates (e.g., X-ray, CT scan, photography) must be completed with day, month, and year.

If there are multiple scan dates associated with an evaluation, i.e., radiological assessments occur over a series of days rather than the same day, the choice of date of assessment could impact the date of progression and/or date of response. If there are multiple scan dates associated with an evaluation, the earliest of the scan dates associated with the evaluation will be used as the date of assessment.

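### Part A's partial-date rule can date a death before the subject was last known alive, and leaves a death with unknown month without an OS event date

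*SAP*

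**What the plan says.** Part A SAP Section 16.2 sets one rule for partial dates in the secondary efficacy endpoints: duration of response, PFS, OS, and response status at 6 and 12 months. It has three parts:

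- For a missing day: "the missing day in a date will be imputed as the 15th of the month, if month and year are documented".
- As a lower limit: "If the imputation is earlier than the date of first study treatment, then the day of first study treatment is taken".
- For anything else: "In all other cases missing or incomplete dates will not be imputed".

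No other part of the Part A SAP deals with partial death dates. The incomplete-date rules in Section 11 cover disease history, adverse events and medications only.

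Section 16.2.3 computes OS from the date of death. Its censoring rule reads: "For subjects who are still alive at the time of data analysis or who are lost to follow up, OS time will be censored". Sections 16.2.1 and 16.2.2 count a death as an event only if it falls within 12 weeks of the last tumor assessment (for PFS, of that or the first dose, whichever is later).

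The Part B SAP, Section 11, has a separate death-date rule. A partial date becomes the later of last contact and the first of the known month, or 1 January if the month is also unknown. For a missing date: "If the date is completely missing it will be imputed as the day after the date of last contact".

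**The concern.** An imputed date should not contradict data already held on the same subject. In Part A the date last known alive is collected (Section 11, data handling after cut-off) and is the basis for OS censoring (Section 16.2.3), yet the imputation of a death date ignores it. Following the rule exactly can therefore record a death on a day when the subject was demonstrably alive.

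Two things are at stake. The first is the OS time of the subjects concerned and, through the 12-week window, whether some deaths count as PFS or duration-of-response events at all. The second is that a subject known to be dead, but with no month of death, has neither an event date nor a stated handling in OS. The current protocol (Section 7.1.5) continues quarterly survival follow-up for up to 5 years after the last subject's last dose, so later Part A OS updates would meet the same rule.

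**Working it through.** No stated figure in the plan depends on this rule, so there is none to reproduce. The check applies the Part A and Part B rules to the same dates. All calendar dates below are assumed for illustration, with first dose on 5 January 2015. Times use the SAP's formula, (end date − first dose + 1)/30.4375 months, and 12 weeks is 84 days.

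**Rules as coded**
- Part A: the later of the 15th and first dose if only the day is missing; otherwise no date.
- Part B: the later of last contact and the first of the month (or 1 January); the day after last contact if the date is fully missing.

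**Largest gap.** Last known alive on the 31st, imputed death on the 15th: 31 − 15 = 16 days, and 16/30.4375 = 0.53 months.

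**Example 1: OS.** Last known alive 27 March, death recorded as March 2015.
- Part A gives 15 March: (69 + 1)/30.4375 = 2.30 months, 12 days before the subject was last known alive.
- Part B gives 27 March: (81 + 1)/30.4375 = 2.69 months, the earliest value consistent with the data.

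**Example 2: the 12-week window.** No IERC progression, last scan 1 March, last known alive 28 May, death recorded as May 2015.
- Part A gives 15 May, day 75 after the scan. As 75 ≤ 84, this is a PFS event at (130 + 1)/30.4375 = 4.30 months.
- The subject was alive on day 88. As 88 > 84, every possible death date is outside the window, and Table 3 requires censoring at the scan: (55 + 1)/30.4375 = 1.84 months.
- For a responder, the same window governs duration of response.

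**Example 3: month unknown.** Last contact 27 March, death recorded only as 2015.
- Part A gives no date. The OS formula cannot be evaluated, and Section 16.2.3 censors only subjects who are alive or lost to follow-up, so no rule covers this subject.
- Part B gives 27 March: 2.69 months.

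**How often a day-missing death would get an impossible date.** Assume the day of death d is uniform over a 31-day month and the last contact is uniform over 0 to w days earlier (gap g). The date is impossible when d − g > 15, and there are 31 × (w + 1) pairs (d, g).

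| w (days) | Impossible pairs / all pairs | Share |
|---|---|---|
| 7 | 100 / 248 | 40% |
| 14 | 135 / 465 | 29% |
| 30 | 136 / 961 | 14% |
| 90 | 136 / 2821 | 5% |

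Two-weekly visits on treatment correspond to w near 14, and quarterly survival contact after treatment to w near 90.

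**The case against.** **Size and importance.** Part A SAP Section 11 declares all secondary analyses exploratory, the confirmatory ORR test does not use these dates, and the documents give no count of partial death dates. Once subjects are on quarterly contact, the share of day-missing deaths affected may be near 5%. All of this stands and limits the weight of the point. It does not make the rule correct for the subjects it reaches.

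**The Part B rule is not uniformly more accurate.** With last contact in an earlier month, it moves a death on the 31st to the 1st, 30 days early against 16 under the mid-month rule. This stands, and it is a reason to keep the 15th where the last-alive date does not bind.

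**Stronger readings that a reader might infer.**
- *A death imputed to 15 March could displace a progression on 24 March in PFS.* Part A SAP Table 3 takes the progression date whenever the IERC records progression and consults death only otherwise. Protocol Table 9 uses the same order for PFS and duration of response. The first-event wording in SAP Section 16.2.1 is looser for duration of response, but the PFS example fails.
- *The rule shortens survival.* Deaths in the first half of a month are moved later, and the 15th is close to the mid-point. The defect is the missing lower limit, not a one-directional bias.
- *Undated deaths are censored as alive.* The SAP does not say this. It is silent, so the supportable statement is that no event date exists.
- *Each undated death costs 1/88 = 1.1 points of OS.* That is only a rough ceiling without other censoring. The effect on a Kaplan-Meier estimate depends on the number at risk and on handling that the SAP leaves open.

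**Conclusion.** The point holds in a limited form. Section 16.2 states a rule that, followed as written, can place a death up to 16 days before the subject was last known alive. It can reverse the 12-week decision for PFS and duration of response when there is no IERC progression, and it leaves a known death with unknown month or no date without an OS event date. This follows from the text alone. The dates in the examples and the 5% to 40% range rest on the stated assumptions.

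The overall effect on the Kaplan-Meier estimates is unknown: it is nil if every death date is complete, and otherwise confined to the partial ones. The documents do not support a claim of systematic bias in either direction, or any effect on the primary endpoint. The correction is still worth making, because the rule produces a wrong result from data already collected and the same sponsor's Part B plan avoids it.

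**What to change.** Add a death-date paragraph to Part A SAP Section 16.2:

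1. Day missing: the later of the 15th of the known month and the last date known alive. The first-of-month version from Part B is an acceptable alternative to the 15th.
2. Month missing: the later of the last date known alive and 1 January of the known year.
3. Date fully missing: the day after last contact, as in Part B.

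In Example 2, step 1 gives 28 May, day 88, and the subject is correctly censored at the scan.

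The cost is one paragraph and a small programming change. No new data are needed, and Section 11 already requires imputed values to be flagged in listings. The downside is that dates set at last contact or 1 January tend to be early. In PFS and duration of response they can also fall inside the 12-week window when the true date did not. If any such dates occur, report how many, and repeat the affected analyses with those deaths at the latest date consistent with the record.

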16.2.1 Duration of Response (IERC)

The duration of response will be calculated for each subject with a confirmed response according to RECIST 1.1 as the time from first observation of response until first observation of documented disease progression or death when death occurs within 12 weeks of the last tumor assessment, whichever occurs first. Details on determination of the first disease progression date are specified in the IERC charter. For subjects with a confirmed response but neither documented disease progression nor death within 12 weeks after the last tumor assessment, as of the cut-off date for the analysis, the duration of response will be censored at the date of the last adequate tumor assessment.

Duration of response = (date of PD or death – date of objective response + 1)/30.4375 (months).

The Kaplan-Meier method will be used to estimate parameters for duration of response. Kaplan-Meier estimates (product-limit estimates) will be presented together with a summary of associated statistics including corresponding two-sided 95% CIs. In particular, the proportion of duration of responses at 3, 6 and 12 months will be estimated with corresponding two-sided 95% CIs. The CIs for the median will be calculated according to Brookmeyer and Crowley (2) and CIs for the survival function estimates at the above defined time points will be derived using the log-log transformation according to Kalbfleisch and Prentice (3) (CONFTYPE = loglog default option in SAS PROC LIFETEST). The estimate of the standard error will be computed using Greenwood's formula.

16.2.2 Progression Free Survival (IERC)

The PFS time, according to the RECIST 1.1, will be defined as time from first administration of trial treatment until first observation of PD or death when death occurs within 12 weeks of the last tumor assessment or first administration of trial treatment (whichever is later). Details on determination of the first disease progression date are specified in the IERC charter.

Specific censoring rules are defined in Table 3 and Table 4. Last adequate tumor assessment is defined as the last tumor assessment result that is not “NE” or “NA”.

PFS time (in months) is defined as:

(date of PD or death - date of the first dose of study treatment + 1)/30.4375 (months).

For subjects with both of the following conditions fulfilled, the general censoring rules apply as presented in Table 3.

- Baseline tumor assessment
- At least one adequate tumor assessment after start of treatment

Table 3 General Censoring Rules for Progression-free Survival

| | | | Date of event / censoring | Censoring |
|--|---|-----|--|------------------|
| PD according to RECIST as assessed by the IERC | | | Date of PD | No |
| No PD | Death within 12 weeks after last tumor assessment or date of first study treatment (whichever is later) | Yes | Date of death | No |
| | | No | Date of last adequate tumor assessment | Yes |

IERC=Independent Endpoint Review Committee, PD=progressive disease.

For subjects with no tumor assessment at baseline or no tumor response assessment post-baseline, the special censoring rules as presented in Table 4, which overrule the general censoring rules, apply.

Table 4 Special Case Censoring Rules for Progression-free Survival

| | | | Date of event / censoring | Censoring |
|--|---|-----|----------------------------------|------------------|
| No tumor assessment at Baseline | Death within 12 weeks after first study treatment | Yes | Date of death | No |
| | | No | Date of first study treatment | Yes |
| No tumor response assessment post Baseline | Death within 12 weeks after first study treatment | Yes | Date of death | No |
| | | No | Date of first study treatment | Yes |

The analysis of PFS will be performed using a Kaplan-Meier method with the same approach as for duration of response described in Section 16.2.1. Kaplan-Meier estimates (product-limit estimates) will be presented together with a summary of associated statistics including corresponding two-sided 95% CIs. In particular, the proportion of PFS at 3, 6 and 12 months will be estimated with corresponding two-sided 95% CIs.

The PFS time will also be presented in a subject listing.

16.2.3 Overall Survival

The overall survival (OS) time will be defined as the time from first administration of trial treatment until the date of death.

For subjects who are still alive at the time of data analysis or who are lost to follow up, OS time will be censored at the last recorded date that the subject is known to be alive (date of last contact, last visit date, date of last trial treatment administration or date of last scan, whichever is the latest) as of the data cut-off date for the analysis.

OS = (date of death – date of the first dose of study treatment + 1)/30.4375 (months).

The analysis of OS time will be performed using a Kaplan-Meier method with the same approach as for duration of response described in Section 16.2.1. Kaplan-Meier estimates (product-limit estimates) will be presented together with a summary of associated statistics including corresponding two-sided 95% CIs. In particular, the proportion of overall survival at 3, 6 and 12 months will be estimated with corresponding two-sided 95% CIs.

The OS time will also be presented in a subject listing.

16.2.4 Response Status at 6 and 12 Months after Start of Study treatment

The response status at 6 and 12 months after start of study treatment according to RECIST 1.1 (as determined by the IERC) will be determined. A subject will be considered to be in response at the given time point (6 or 12 months after start of study treatment) if the subject had a documented response (PR or CR) prior to that time point, and did not have any of the following events up to the given time point:

- death
- documented disease progression according to the RECIST 1.1,
- lost to follow-up
- withdraw consent

The proportion of subjects with response at 6 and 12 months after start of study treatment will be calculated as the proportion of subjects in response among all subjects that have started study treatment at least 6 (12) months prior to the time of the analysis, respectively. Clopper-Pearson 95% CIs will be reported as well.

In addition, durable response rate will be summarized for the ITT analysis set. Durable response rate (DRR) is defined as the proportion of subjects with an objective response in terms of CR or PR according to RECIST 1.1, as determined by the IERC, with a duration of at least 6 months. Clopper-Pearson 95% CIs will be reported for the DRR as well.

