7.1.2.1 Part A

During the treatment period, the following assessments will be performed (see [Appendix I](#) for the detailed schedule):

- The EQ-5D and FACT-M will be completed by subjects prior to any study related procedures at Week 7, and then once every 6 weeks thereafter while on treatment.
- Subject interviews (optional) by a trained experienced interviewer to collect subjects' current experience with their disease and its treatment (at Week 13 and at 6 months of treatment, see [Section 7.7.1](#)).
- AEs and concomitant medications will be documented at each trial visit.
- ECOG PS will be assessed at Day 1 (unless the Screening ECOG PS was performed within 3 days prior to Day 1) and at each study visit thereafter.
- Physical examinations will be performed at each treatment visit until Week 13 and every 6 weeks thereafter. Such examinations will include a comprehensive skin examination for tumor.
- Vital signs and body weight will be assessed in each treatment visit.
- A 12-lead ECG (assessed prior to infusion and 2 hours \pm 20 minutes after the end of infusion) will be assessed at each treatment visit up to and including Week 13, and every 6 weeks thereafter until 18 months, after which subjects no longer require on treatment ECGs.
- The laboratory hematology, hemostaseology will be assessed at each visit. Core serum chemistry tests will be assessed at Weeks 1, 7, 9, and 11 and after Week 13, every 2 weeks thereafter and full serum chemistry (including core chemistry) will be assessed at Weeks 3, 5, and 13 and then every 6 weeks thereafter. In addition, for subjects with liver metastases at Baseline, samples for ALT, AST, total bilirubin, and alkaline phosphatase determination will be collected at Weeks 2, 4, and 6. A basic urinalysis (dipstick) will be performed at each on treatment visit. If the basic urinalysis is abnormal, a full urinalysis should be performed.
- A urine β -HCG pregnancy test will be performed at each treatment visit (before each administration of the study drug) for females of childbearing potential.
- Tumor evaluation (see [Section 7.3](#)) will be performed at Week 7, and then once every 6 weeks thereafter, with a tumor assessment visiting time window of 5 days prior to dosing. After Week 55 (12 months) from the first treatment, tumor assessments will be every 12 weeks.

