On these grounds, the expression of PD-L1 by the immune infiltrating cells as well as the expression of PD-L1 at the surface of MCC constitute a very strong rationale for the evaluation of avelumab in that disease. Extrapolation of the response rate observed with the Genentech PD-L1 (up to 80% in PD-L1+ tumor cells and up to 80% in patients with more than 10% of the tumor infiltrating cells expressing PD-L1) suggest that a clinically significant overall response rate can be expected from anti PD-L1. Since a response rate of approximately 20% has been reported in several tumor types where only a fraction of the tumors express PD-L1 at the surface of the tumors or at the surface of immune infiltrating cells, it is considered that an expected response rate of 35% is a reasonable hypothesis.

8 Overview of Planned Analyses

This SAP covers the analyses for efficacy and safety based on the data cut-off dates for the interim and final analyses. Statistical analyses will be performed using cleaned eCRF data gained until a clinical cut-off date. It also includes detailed analysis for pharmacokinetics and immunogenicity data analysis.

For the interim futility analysis, the clinical cut-off date will be the date 3 months after start of study treatment of the 20th subject; for the interim efficacy analysis, the clinical cut-off date will be the date 6 months after start of study treatment of the 56th subject; for the primary analysis, the clinical cut-off date will be 6 months after start of study treatment of the last subject enrolled in the trial.

The Safety Monitoring Committee (SMC) will be responsible for reviewing the interim futility and efficacy analysis as well as the primary analysis. A SMC data report plan will be created separately to specify what analysis results will be distributed to SMC for review for each of the

interim analyses and the primary analysis. There will be no unplanned interim analyses, with the exception of the ongoing safety monitoring during the trial.

Further separate SAPs will cover the following analyses:

CCI

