8.3 Final Analysis

All planned analyses outlined in this SAP will be performed for the primary analysis. A partial database lock will be performed for the primary analysis and the last planned SMC meeting will

be held thereafter. The full DB lock will take place one year after the last subject receives the last dose of avelumab.

In addition, no database can be locked until this SAP has been approved.

Subject follow-up for progression and survival will continue until 1 year after the last subject receives the last dose of avelumab.

9 Changes to the Planned Analyses in the Clinical Trial Protocol

The statistical methods as described in the protocol of the trial were adopted. Additional statistical analyses and summary performed that are not included in the CTP are summarized in details in Section 5.1 Changes to Previous Version.

10 Analysis Sets

Screening Analysis Set

The screening analysis set includes all subjects who signed the informed consent.

Intent-to-Treat Analysis Set

For the interim futility and the interim efficacy analysis, the intention-to-treat (ITT) analysis set includes the first 20 and 56 subjects who received at least one dose of trial treatment, respectively. For the primary analysis, the ITT analysis set includes all subjects who received at least one dose of trial treatment.

The ITT analysis set will be used for all analyses of efficacy, and health-related quality of life and will be the primary population for decision-making.

Safety Analysis Set

The Safety analysis set includes all subjects who received at least one dose of trial treatment at the clinical cut-off date. The Safety set will be used for all safety analyses.

Per Protocol Analysis Set

The Per-Protocol (PP) analysis set is a subset of the ITT analysis set and includes all ITT subjects who meet all of the following criteria:

- Measurable disease per RECIST 1.1 and IERC assessment
- Distant metastatic disease
- Histologically proven MCC with confirmation of the diagnosis by immuno-histochemistry detection of CK20 (or other appropriate cytokeratin expression such as pancytokeratin,

AE1/AE3, or Cam5.2) according to the assessment documented in the “Disease History” eCRF page

- Have progressed after 1 line of chemotherapy that was administered for the treatment of distant metastatic MCC as defined in Section 5.3.1 Inclusion Criteria in the protocol

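### Part A reports a durable response rate on all treated subjects at a cut-off when the last-enrolled cannot yet have a 6-month response; if unfinished responses count as not durable, the rate is biased low.

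*SAP*

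**What the plan says.** The Part A SAP (version 3.0) defines DRR in Section 16.2.4 as the proportion of subjects with an objective response by independent review that lasts at least 6 months. On the denominator it says "In addition, durable response rate will be summarized for the ITT analysis set", and on the interval "Clopper-Pearson 95% CIs will be reported for the DRR as well". Section 10 makes the ITT set at the primary analysis every subject dosed; Section 7 records 88.

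On timing, Section 8.3 says "All planned analyses outlined in this SAP will be performed for the primary analysis", and Section 8 says "the clinical cut-off date will be 6 months after start of study treatment of the last subject enrolled". Section 11 excludes tumor data after the cut-off.

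Section 16.2.1 counts duration of response (DR) from first response and censors an ongoing response at the last adequate tumor assessment. Protocol 7.1.2.1 puts the first scan at Week 7, then every 6 weeks.

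The paragraph just before the DRR text in 16.2.4, on response status at 6 and 12 months, limits its denominator: "among all subjects that have started study treatment at least 6 (12) months prior to the time of the analysis". The DRR has no such limit.

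Part B treats the same endpoint differently. Protocol 8.3.1 and Section 16.1 of the Part B SAP count a response censored before 6 months as a failure. The Part B cut-off is 15 months after the last first dose, and Section 8.2 of the Part B SAP skips DRR at the early interim for want of data.

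**The concern.** Six months of follow-up from first dose cannot contain six months of response first seen at Week 7. Subjects treated late in accrual are in the denominator but cannot enter the numerator, however well they are doing. An exact binomial interval needs every subject classed as success or failure, so the natural reading is that an ongoing response censored before 6 months counts as not durable. The DRR then understates what complete follow-up would show, and the nominal 95% interval under-covers that value. Section 5 of the SAP says its planned analyses will go into regulatory submissions or manuscripts, where nothing would show that some subjects had no chance to qualify.

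**Working it through.** **Plan's own figures.** The plan gives no DRR figure for Part A. The nearest figures belong to the ORR test, and they reproduce: P(X ≥ 20 | 56, 0.20) = 0.0045, P(X ≥ 26 | 88, 0.20) = 0.0211, overall rejection probability 0.0223. None depends on the DRR.

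**When a response can qualify.** SAP 16.2.1 gives DR = (end − first response + 1)/30.4375. DR ≥ 6 needs at least 6 × 30.4375 = 182.6, that is 183 days. A response first seen on Day r qualifies on Day r + 182 at the earliest. For the last subject the cut-off is about Day 183, so r would have to be Day 1.

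- Scheduled scans fall on Days 43, 85, 127, 169, 211, 253 and so on. The longest DR for the last subject is (169 − 43 + 1)/30.4375 = 4.17 months. At the limits of the visit windows it is (170 − 38 + 1)/30.4375 = 4.37.
- A Week 7 response is first long enough at the Day 253 scan (Day 248 with the 5-day window). Even a Day 38 response scanned on Day 212 has only 175/30.4375 = 5.75 months.
- Unscheduled scans, allowed by Protocol 7.3 and SAP Section 11, shorten the wait: a Day 43 response qualifies on Day 225, a Day 29 response on Day 211. Both are after Day 183.

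**Share of subjects who cannot qualify.** Accrual length is not stated. The Protocol Synopsis plans the first subject in Q3 2014, and SAP version 2.1 of 17 November 2015 already records 88 treated. From 1 July 2014 that is 504 days (16.56 months); from 30 September 2014 it is 413 days (13.57 months). With uniform accrual:

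| First qualifying day | 16.56 months | 13.57 months |
|---|---|---|
| 253 (scheduled) | 14.0% | 17.0% |
| 248 (scheduled, window) | 13.0% | 15.8% |
| 225 (unscheduled) | 8.4% | 10.3% |
| 211 (unscheduled) | 5.6% | 6.9% |

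Shorter accrual raises every share.

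**Size, closed form.** Take ORR 35% (SAP Section 7), exponential DR after confirmation and scheduled scans only. A Week 7 response confirmed at Day 85 is durable if it is progression-free through the Day 211 scan, 126 days or 4.14 months after confirmation. Complete-follow-up DRR = 0.35 × 2^(−4.14/median): 27.6% for a median of 12 months, 31.1% for 24.

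- All responses at Week 7: (253 − 183)/504 = 13.9% of subjects are lost, a shortfall of 3.8 and 4.3 points.
- 75/20/5% of responses at Weeks 7/13/19: the average wait past Day 183 is 0.75×70 + 0.20×112 + 0.05×154 = 82.6 days. 82.6/504 = 16.4%, a shortfall of 4.5 and 5.1 points.

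**Size, simulation.** n = 88, 5,000 runs, cut-off tied to the actual last subject, censored DR below 6 months counted as failure. Tying the cut-off to the actual last entry makes the shortfall slightly larger than the closed form.

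| Response timing | Accrual (months) | Median DR (months) | Complete DRR | DRR at cut-off | Exact CI coverage | ORR × KM coverage |
|---|---|---|---|---|---|---|
| All Week 7 | 16.56 | 3 | 13.4% | 11.5% | 94% | 96% |
| All Week 7 | 16.56 | 6 | 21.7% | 18.4% | 90% | 95% |
| All Week 7 | 16.56 | 12 | 27.6% | 23.5% | 91% | 95% |
| All Week 7 | 16.56 | 24 | 31.1% | 26.3% | 88% | 95% |
| 75/20/5 | 16.56 | 3 | 13.4% | 11.0% | 93% | 96% |
| 75/20/5 | 16.56 | 6 | 21.7% | 17.9% | 89% | 96% |
| 75/20/5 | 16.56 | 12 | 27.6% | 22.6% | 87% | 95% |
| 75/20/5 | 16.56 | 24 | 31.1% | 25.5% | 83% | 96% |
| All Week 7 | 13.57 | 12 | 27.6% | 22.6% | 87% | 95% |
| All Week 7 | 13.57 | 24 | 31.1% | 25.4% | 83% | 95% |
| 75/20/5 | 13.57 | 12 | 27.6% | 21.7% | 82% | 95% |
| 75/20/5 | 13.57 | 24 | 31.1% | 24.5% | 77% | 96% |

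A separate simulation assumed accrual of 9 to 16 months, responses split 75/15/10% at Weeks 7/13/19, and 80% of responses lasting 6 months. It gave 19.5% to 23.3% against a complete-follow-up 28.5%.

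**At the analysis 12 months after last accrual** (16.56 months of accrual, 3,000 runs) the shortfall is at most 0.1 points and exact-interval coverage is 95.4 to 96.7%.

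**The case against.** The Part A SAP contains no failure rule, so what the text proves is an omission; the downward bias follows on one reading. That stands as a condition. It does not rescue the plan, because counting censored responses as durable would bias the rate upward instead.

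The DRR could also be read as a plain count of 6-month responses documented by the cut-off. Complete-follow-up DRR is then a target the SAP never names, and a footnote on follow-up might be enough. That is a fair reading of the point estimate. A 95% interval, however, invites inference about the underlying rate, and the rate documented by this cut-off depends on how fast the trial accrued.

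Much is already planned. SAP Section 7 schedules an analysis of secondary and exploratory endpoints at 12 months, where the bias nearly vanishes, and 16.2.1 plans Kaplan-Meier DR: "In particular, the proportion of duration of responses at 3, 6 and 12 months will be estimated with corresponding two-sided 95% CIs". Both soften the harm. But nothing holds the DRR back for the 12-month analysis, and the Kaplan-Meier estimate describes responders only, so it corrects neither the DRR nor its interval.

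The size is not derived from the documents alone. Accrual length and pattern, DR distribution and response timing are assumed, and the shares who cannot qualify include non-responders. At 4 to 5.5 points, about 4 to 5 of 88 subjects are involved. The Part B interim is only a loose parallel, since it comes 3 months after the 25th subject. These points limit the precision of the estimate; the direction is unaffected.

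**Conclusion.** The concern holds and is minor. That a late entrant cannot show a 6-month response at the primary cut-off follows from the documents' dates and formula and needs no assumption. The downward bias needs one: that responses censored before 6 months are counted as not durable.

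The size is illustrative. At 16.6 months of accrual it is about 4 to 5.5 points for median DR of 12 to 24 months (coverage 83 to 91%), 3.3 to 3.8 points at a median of 6 months, and 2.0 to 2.4 points at 3 months. At 13.6 months of accrual it is 5.0 to 6.5 points for medians of 12 to 24 months. Unscheduled scans would reduce these figures; later first responses would raise them (5.8 to 6.6 points with 50/30/15/5% at Weeks 7/13/19/25 and 16.6 months of accrual).

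No decision rests on the result. SAP Section 11 makes everything except the ORR test exploratory, the error is conservative, and type I error is unaffected.

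**What to change.** Amend Section 16.2.4 of the Part A SAP in three ways:

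1. At the primary analysis, estimate DRR as confirmed ORR × the Kaplan-Meier probability of DR of at least 6 months, with a bootstrap interval or a delta-method interval on the logit scale.
2. Report the simple ITT proportion with its Clopper-Pearson interval at the analysis 12 months after last accrual.
3. State how responses censored before 6 months are counted.

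The cost is a few sentences and a few lines of programming, with no new data. The interval at the primary analysis is no longer exact binomial, and the Kaplan-Meier step assumes non-informative censoring. In the simulations above, ORR × Kaplan-Meier was within 0.2 points of the complete-follow-up DRR with 94.7 to 96.1% coverage.
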